11.1 Definition of AE

An adverse event is any symptom, sign, illness or experience which develops or worsens in severity during the course of the study. Intercurrent illnesses or injuries should be regarded as adverse events. Abnormal results of diagnostic procedures are considered to be adverse events if the abnormality:

- Results in study withdrawal
- Is associated with clinical signs or symptoms
- Leads to treatment or to further diagnostic tests
- Is considered by the investigator to be of clinical significance

11.2 Definition of SAE

Adverse events are classified as either serious or non-serious. A serious adverse event is any event that results in:

- Death, Life-threatening situation
- Hospitalization or prolongation of hospitalization
- Disability or incapacitation
- Other events determined by investigator to be medically significant in which subject's well-being is jeopardized (e.g. events that have high likelihood of escalating to the point of meeting criteria outlined above)

11.2.1 Clinical Laboratory Abnormalities & Other Abnormal Assessments as AEs & SAEs

Any new abnormal, vital, examination, or laboratory finding judged clinically significant by the investigator will be documented as an AE or SAE, if meeting the definitions for such. Abnormal lab findings or other abnormal assessments associated with the disease under study will not be considered AEs or SAEs unless more severe than expected, as judged by the investigator.

11.2.2 Time Period and Frequency of Detecting AEs and SAEs

Upon consenting, a subject is considered to be a participant in the study, and until that person either withdraws or completes study, AEs and SAEs will be recorded. The investigational team will promptly report any AE/SAE as required per federal guidelines.

11.2.3 Device Failures and Malfunctions

Device Quality Control. All failures and malfunctions of the device will be documented.

12 Data Analysis and Statistical Considerations

12.1 Statistical Analysis Overview

The population demographics (age, gender, etc.) and clinical values (vital signs, labs etc.) will be reported using the appropriate summary measures (e.g. mean, standard deviation, and proportions).

12.2 Statistical Analysis of Primary and Secondary Endpoints

Primary Endpoints: We will utilize immunoassay to analyze the CSF samples to determine the levels of Insulin concentration at the specified times. We will graph these values across time for each subject using line graphs. We will also graph the sample average Insulin concentration across time, and at different doses with error bars and report concentrations as mean \pm SE. Finally, the concentrations will be analyzed using common pharmacokinetic measures including the peak concentration (Cmax), time to peak concentration (Tmax), and area under the curve (AUC). This type of analysis is very similar to that done in Dhuria's 2009 publication in the *Journal of Pharmaceutical Sciences*, on which [name] and [name] were co-authors. Similar analysis will be conducted for secondary endpoints.

AEs and SAEs will be categorized and summarized by study group. We will descriptively note if any group was more likely to have experienced a particular AE/SAE or generally experienced more AEs/SAEs throughout the course of the study.

13 Study Conduct Considerations

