Appendix G.	Insulin Stability Experiment Report & Raw Data	32

List of Tables

Table 1: REDACTED	Error! Bookmark not defined.
Table 2: Study Design.....	9
Table 3: Study Visit Schedule	15
Table 4: Prohibited Medications.....	17

List of Figures

REDACTED

Definitions

Adverse event (AE)	Any undesirable patient experience that may include but is not limited to an abnormal sign, symptom, illness, abnormal laboratory value, or other medical event.
Cerebrospinal Fluid (CSF)	Clear liquid that flows around the brain and spinal cord.
Columbia-Suicide Severity Rating Scale (C-SSRS)	A scale designed to quantify the severity of suicidal ideation and behavior.
Data Safety Officer (DSO)	An independent individual with relevant experience assigned to review safety data to monitor for incidence of trends that would warrant termination of the trial.
Intranasal (IN)	A method of drug delivery that is particularly applicable to delivering centrally acting medications into the central nervous system.
Intranasal Insulin (INI)	Human insulin that is administered to the nose in effort to directly target delivery to the central nervous system
Lumbar Puncture (LP)	A medical procedure which involves inserting a needle between two vertebrae of the lower back to collect fluid surrounding the spinal cord and brain.
Serious adverse events (SAE)	Any symptom, sign, illness or experience that develops during the study and results in a life-threatening situation, hospitalization, significant disability, and other events determined by the investigator to be significant.

Protocol Summary

PROTOCOL TITLE	Measurement of Insulin Levels in CSF of Healthy Adults after a Single Intranasal Dose
SHORT TITLE	INI-CSF
STUDY PHASE	Phase I
STUDY OBJECTIVES AND PURPOSE	

Primary Objectives:
 
• To measure the concentration of insulin that reaches central nervous system in humans after intranasal administration	

Secondary Objectives:
 
• To describe the effect of single intranasal insulin dose on serum insulin in healthy adults	
STUDY DESIGN	
Study Type	Pharmacokinetics
Control Type	None
Study Indication Type	Pharmacokinetics
Blinding Schema	Unblinded
Study Drug	Regular, Human Insulin [rDNA origin] USP solution for injection 100 units/mL
Device	SipNose
Route	Intranasal
Study Design	Open-label, randomized
Planned Duration of Subject Participation	4-5 weeks (Treatment duration: 1 dose)
PRIMARY ENDPOINTS	

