4.1 Primary Endpoints

- Cerebrospinal Fluid Insulin Levels at pre-defined times (0-40Min)

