7.1.2.1 Fluoroscopy-Guided Lumbar Puncture Procedure

CSF samples will be collected according to standard operating procedures for fluoroscopy-guided lumbar puncture as observed by the General Radiology department at Regions Hospital. The procedure will be performed by a trained clinician (i.e., an interventional radiologist or an experienced member of their team), who will obtain verbal consent (in addition to the research informed consent obtained/documentated at Visit 1). CSF will be collected serially using gravity drainage. Sterile extension tubing connected to the LP needle will dispense CSF into sterile collection tubes for pharmacokinetic analysis. Samples will be collected at 5 times: once prior to the administration of a single dose of intranasal insulin and at once each at 10, 20, 30, and 40 minutes post-drug administration. Approximately 1-2ccs of CSF will be collect at all 5 time points for a total of 10ccs of CSF. The tubing connected to the needle will be flushed out between sample collections to avoid contamination between specimen timepoints. The subject will lie in prone position throughout the procedure with appropriate measures taken to minimize discomfort (e.g., provision of warm blankets, use of positioning sponges, etc.).

Subjects will lie on their back 2 hours after the procedure for standard-of-care monitoring with nursing staff, and periodic collection of vital signs. Participants will receive instructions from the clinical team on techniques for preventing and treating post-LP headache (e.g., drinking water and caffeinated beverages, using over-the-counter pain medications). They will also receive guidance on when to seek additional help for their headache and/or any other emergent symptoms requiring immediate medical attention such as fever, persistent headache, and weakness/numbness of the lower extremities. Subjects will receive a safety assessment phone call from study staff 1 day after the procedure.

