7.3.11.1 CSF Sampling

It is our intention to collect samples at pre-defined times following a single dose administration. CSF will be collected at 0, 10, 20, 30 and 40 minutes for all study participants. CSF samples will be assessed for insulin using a one-step sandwich immunoassay with a limit of detection of 0.1 µIU/ml or 0.7 pmol/L

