10.2 Subject Withdrawal

Subject may withdraw from study at any time for any reason without penalty or be terminated from the study by the clinical investigator (see provisions for termination by study team.) Investigational team will

document the reason(s) for withdrawal. In the event a subject chooses to withdraw from study before Visit 3, the safety procedures described in 7.3 will be performed (ideally within 3 days following subject's decision to withdraw). For all subjects who withdraw, all final safety assessments will be collected as possible regardless of time elapsed since previous visit. In addition to the termination visit, subjects who withdraw early will be contacted within 7 days by study staff via telephone to assess development of new and/or ongoing AEs and concomitant medications. Efforts will be made to recruit subjects to replace any withdrawals before lumbar puncture (or subjects for whom we are unable to get sufficient for analysis) so as to maintain n=6 per group.

Subject's participation may be terminated at the discretion of the investigator. Individuals may be withdrawn for the following reasons:

- Clinically significant adverse events
- Lost to follow-up
- Protocol violations
- Inability to tolerate study medication
- Other

11 Adverse Events (AE) and Serious Adverse Events (SAE)

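### Section 12.2 reports Cmax and Tmax as the largest of five raw readings and its time, with nothing to tell a chance peak from delivered insulin

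*Combined protocol and SAP*

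**What the plan says.** Section 7.3.11.1 fixes the sampling: "CSF will be collected at 0, 10, 20, 30 and 40 minutes for all study participants". Section 7.1.2.1 makes the first of the five a pre-dose sample, taken "once prior to the administration of a single dose of intranasal insulin". The primary endpoint in Section 4.1 covers the whole window, including time 0: "Cerebrospinal Fluid Insulin Levels at pre-defined times (0-40Min".

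Section 12.2 then analyses the concentrations by "common pharmacokinetic measures including the peak concentration (Cmax), time to peak concentration (Tmax") and AUC. It also plans a line graph for each participant and a mean curve with standard errors: "We will also graph the sample average Insulin concentration across time, and at different doses with error bars". Serum is to be analysed in a similar way.

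The Protocol Summary gives "Control Type None". Section 10.2 plans replacements "so as to maintain n=6 per group", so 12 participants in all.

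Section 12.2 states no baseline subtraction, no pre/post contrast, no interval or test, no criterion for a real rise, and no rule for values below the limit of detection that Section 7.3.11.1 gives (0.1 µIU/mL).

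**The concern.** The drug is regular human insulin and the assay is an insulin immunoassay. The documents describe no way to separate dosed from native insulin. A participant with detectable native insulin therefore has a Cmax and a Tmax whether or not any drug arrives. The largest of several noisy readings lies above the true level on average, and with four of the five sampling times after the dose it will usually fall after the dose.

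Section 5.1.2 gives the key objective as learning whether the device can target insulin to the brain and spinal cord. That is a question about delivery. A result such as 10 of 12 participants peaking after dosing, with mean Tmax near 20 minutes, could be read as an answer to it. Nothing in Section 12.2 would tell the reader that noise alone can produce the same result.

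**Working it through.** The plan gives no power, SD, effect size or chance rate, so there is no figure of its own to reproduce. The inputs are five sampling times (7.3.11.1), one of them pre-dose (7.1.2.1), and 6 participants per dose (10.2). Throughout, SD means the within-participant SD of a single reading, which the documents do not give.

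**Reference case (assumed): no delivery, flat true level, five exchangeable readings without ties**

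- Each time is the maximum with probability 1/5, whatever the size or shape of the noise.
- P(Tmax > 0) = 4/5 = 80%.
- Mean Tmax = (0 + 10 + 20 + 30 + 40)/5 = 20 min. Among those with Tmax > 0 it is (10 + 20 + 30 + 40)/4 = 25 min.
- Expected post-dose peaks: 0.8 × 6 = 4.8 per dose and 0.8 × 12 = 9.6 overall.
- Binomial(12, 0.8): P(at least 9) = 0.795, P(at least 10) = 0.558, P(12 of 12) = 0.8^12 = 0.069. For one dose, P(6 of 6) = 0.8^6 = 0.262.

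**Size of the upward bias (normal noise, simulated with 10^6 draws)**

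| Summary | Expectation with no delivery |
|---|---|
| Cmax minus true level (maximum of 5) | +1.16 SD |
| Post-dose maximum minus 0 min value (maximum of 4) | +1.03 SD |
| Mean of the 4 post-dose values minus 0 min value | 0 |

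The last two rows use the same baseline, so the bias comes from taking the maximum.

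**Departures from the reference case**

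| Assumption | Peak after dosing | Mean Tmax |
|---|---|---|
| AR(1) correlation 0.3 to 0.95 | 78% to 73% | 20 min |
| Drift −0.5 SD per 10 min | 49% | 8.1 min |
| Drift +0.5 SD per 10 min | 98% | 32.0 min |
| 50% of readings below the limit of detection, ties to first time | 77% | 19.4 min |
| 80% below, ties to first time | 54% | 13.4 min |

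With AR(1) correlation of 0.3 to 0.8, the post-dose maximum minus 0 min averages +0.92 to +0.55 SD. In the censored cases, participants with at least one detectable value stay near 80% and 20 min.

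**Precision of the alternative**

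For independent readings, the mean post-dose value minus the 0 min value has variance SD² × (1/4 + 1) = 1.25 SD². The 95% half-width for one dose (n = 6) is 2.571 × √(1.25/6) = 1.17 SD. For both doses together (n = 12) it is 2.201 × √(1.25/12) = 0.71 SD. Real differences between participants in the change would widen both.

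**The case against.** The strongest reply is that the trial is descriptive. Its objective is to measure concentrations, no decision rests on Cmax or Tmax, and both are standard summaries. Outputs without the selection effect are already planned: each participant's full profile, and the mean with SE at each time and dose, from which a reader can compare pre-dose with post-dose informally. The two randomised doses also allow a comparison in which the maximum-of-five bias is equal in expectation if the noise is equal. All of this stands, and it limits the point to how the results may be interpreted.

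The figures are also conditional. The documents give neither the baseline CSF insulin nor its variability, so it is unknown whether readings will be mostly quantifiable or mostly tied below the limit of detection. Drift is possible: Section 7.3.5 draws laboratory samples regardless of fasting, if that sentence covers the pharmacokinetic samples.

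Some obvious remedies also fail:

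- The number with Tmax > 0 cannot serve as a test. Even 12 of 12 has null probability 0.069.
- A cut-off of 2.77 times the assay SD ignores biological variation. With duplicate means and an assumed biological SD of 1 to 3 times the assay SD, false peaks run from 16% to 54%.
- Dropping participants with no detected peak leaves a summary of selected responders, which is again biased upward.

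What the reply does not remove is that Section 12.2 makes none of the unbiased outputs a stated reference, while Section 5.1.2 asks about delivery.

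**Conclusion.** The point holds as a limit on what Cmax and Tmax can show. Under flat, exchangeable, untied readings, about 80% post-dose peaks, a mean Tmax of 20 minutes and a Cmax 1.16 SD above the true level are what no delivery would look like. Serial correlation changes the first two little; drift or heavy censoring can change them a lot.

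A reader might go further in three ways that the documents do not support:

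- That 80% and 20 minutes are the rates to expect in this trial if no drug arrives. They depend on assumptions that the documents neither confirm nor rule out.
- That the design contains no reference at all. A pre-dose sample and two dose groups exist; they are simply not used as a reference for Cmax or Tmax.
- That Cmax and Tmax should not be reported, or that the plan treats them as proof of delivery. Section 12.2 makes no such claim.

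This is an improvement worth making before the data are seen. It is not a flaw that invalidates the trial.

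**What to change.** In Section 12.2, for CSF and likewise for serum:

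1. Report Cmax and Tmax for all participants, labelled as descriptive only. State that every participant with quantifiable insulin has a maximum, whether or not drug arrives.
2. Base any statement about delivery on within-participant change from the 0 minute sample, by dose, with a confidence interval. Name one measure in advance: mean post-dose minus 0 min, or baseline-corrected AUC.
3. If the post-dose maximum minus 0 min is quoted, show beside it the distribution obtained by permuting the five time labels within each participant, at a stated level. In simulation at a nominal one-sided 5%, this kind of reference rejected about 3-6% of the time with independent readings and up to about 9% with autocorrelation 0.8, so the level is approximate.
4. Do not use the number with Tmax > 0 as a test, do not use an assay-only cut-off to declare peaks, and do not drop participants without a peak.

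The cost is some wording and a short program; no extra sample, visit or participant is needed. The intervals will be wide at 6 per dose, and neither the change from baseline nor the permutation separates drug from other trends over the 40 minutes. The report should say so.

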The most common side effect with INI administration noted is transient local or nasal irritation. In Appendix B, please refer to Table 3 of the Schmid et al., 2018 review for a summary of the local or nasal effects of INI in humans. In 2012, Craft et al reported, that number of adverse events was higher for the 20 IU and 40 IU when compared to the placebo group; however, there were no SAE's and mostly minor AEs such as rhinitis were reported (Table 4, ³⁵). Similar minor AEs were reported in the 2017 by Craft et al using INI (Supplementary table 2, ³⁹). Similar findings were reported in recent meta-analyses⁴⁰ and the most recent trial on INI²⁶, which showed no clinically relevant adverse events during the chronic administration of 40 IU of insulin with two different administration devices. Overall, INI at the proposed dose in this protocol, is expected to be safe with limited side effect profile. We do plan to monitor the subjects for hypoglycemia.

2 Summary of Device Description

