4.3 Safety

- Incidence and severity of serious adverse events (SAEs) and adverse events (AEs)
- Frequency of change in clinically-significant vital signs
- fingerstick glucose level <70mg/dl

5 Study Design

This Phase 1 is a single center, open-label, randomized pharmacokinetic study designed to describe the central nervous system delivery of intranasal insulin to CSF using anIN delivery device.

Table 1: Study Design

INI Insulin Dose	Collection Times
40 IU (n=6) 2 x 200 μ L (0.2ml)	0, 10, 20, 30, 40 min
80 IU (n=6) 2 x 200 μ L (0.2ml) Wait 2 min 2 x 200 μ L (0.2ml)	0, 10, 20, 30, 40 min

After written informed consent has been obtained, subjects will be screened to assess study eligibility based on study inclusion/exclusion criteria. Subjects who are eligible at the end of the screening visit will be randomized and assessed for outcome measures, including lumbar puncture and CSF/blood draw following a single dose of INI administered by the trained research staff. Randomization will be stratified by gender to ensure a balanced distribution of male and female participants within each group. A Block randomization scheme will be employed to ensure that the final group sizes are equivalent.

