5.2 Study Duration

Study participation will last approximately 4-5 weeks, consisting of a screening/baseline visit, treatment/lumbar puncture visit, a follow-up/final assessment visit.

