7.1 Demographic and Baseline Assessments

7.1.1 Screening Visit 1

The following procedures will be performed at this visit: This may also be divided into two parts, with virtual and in-person visits. Virtual activities (e.g., consent, review of medical history/medications) can be completed on a separate day(s) from other study procedures, provided that consent occurs within 3 months of the lumbar puncture and all other screening activities are completed within the specified window (21-7 days prior to lumbar puncture visit/Visit 2). All activities will take approximately 2 hours to complete. No study procedures, virtual or otherwise, will be completed until a fully executed consent form has been obtained. Participants will be given the option to have a dose of sterile saline administered by research staff using the device if they want to experience the sensation of the device before the lumbar puncture visit.

- Obtain written informed consent Review Inclusion/Exclusion Criteria
- Review medical history, as it pertains to inclusion/exclusion criteria
- Pregnancy test for women of childbearing potential
- Review guidance on the use of effective birth control from the time of study enrollment until 30 days **after** the final visit.
- Obtain subject's demographic information (date of birth, gender, race, and ethnicity).
- Collect vital signs, height and weight
- Obtain details of medications taken over the course of the last 30 days
- Physical/neuro examination including examination of the nares and nasal passages
- Blood draw for laboratory investigations
- C-SSRS
- 12-Lead Standard ECG
- Saline test dose (optional)
- Pre-procedure instructions
- Provide Information sheet provided relating to pre-lumbar puncture hydration
- Visit #2 scheduled after 2 weeks \pm 7 days

7.1.2 Lumbar Puncture Visit 2: In-Person Visit (2 week \pm 7 days after Visit 1)

The subject will be check in at the Regions Hospital outpatient care unit (OPCU). The visit will be at the General Radiology Department (where the lumbar puncture will be performed and study data collected) and will return to the OPCU for post-operative monitoring.

The following procedures will be performed at this visit:

- Review Inclusion/Exclusion Criteria
- Collect concomitant medication information and record AEs/SAEs
- Collect vital signs and weight
- Pregnancy test for women of childbearing potential
- Review guidance on the use of effective birth control until 30 days study **after** the final visit.

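### The dose-group AE comparison runs from consent, so events before the single insulin dose can be counted under a dose group; this adds noise and dilutes proportions, but does not favour either dose

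*Combined protocol and SAP*

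**What the plan says.** Section 12.2 summarises AEs and SAEs by study group and will note descriptively if "any group was more likely to have experienced a particular AE/SAE or generally experienced more AEs/SAEs throughout the course of the study". Three other places determine what that period contains.

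- Section 11.2.2 starts the clock at consent: from then "until that person either withdraws or completes study, AEs and SAEs will be recorded". The Study Visit Schedule (the table after section 7.3.11.2) accordingly marks adverse events at Visit 1.
- Section 11.1 ties the definition to the study and not to the drug: "An adverse event is any symptom, sign, illness or experience which develops or worsens in severity during the course of the study". It adds: "Intercurrent illnesses or injuries should be regarded as adverse events".
- Section 7.1.1 places screening 21 to 7 days before Visit 2, where the only insulin dose is given. It also lets participants choose at screening to receive "a dose of sterile saline administered by research staff using the device".

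The safety endpoint in section 4.3 carries no time window. Sections 7.3.1 and 7.3.2 send examination abnormalities found at Visit 1 to medical history. No sentence restricts the group comparison to events after dosing.

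**The concern.** Read as written, section 12.2 assigns an event to a dose group even when the participant had not yet received insulin. A respiratory infection between screening and Visit 2 qualifies as an AE under section 11.1, and so does a nasal symptom after the saline dose. Such events can resemble the drug effect being looked for: section 1.1.3, describing an earlier trial of intranasal insulin, says "mostly minor AEs such as rhinitis were reported". The medical-history rule does not remove them, because it covers examination findings at Visit 1 and not symptoms or illnesses that begin afterwards.

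What is at stake is how clearly a small safety table can be read. With 6 participants per arm and no test or model, readers will interpret the table directly. One participant moves an arm's proportion by 1/6 = 16.7 points.

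**Working it through.** The plan gives no AE rate, power or effect size, so there is no stated figure to reproduce.

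**1. Calendar time before insulin.** Inputs: screening to dose 7 to 21 days, nominally 14 (sections 7.1.1 and 7.1.2); dose to Visit 3 about 7 days, ± 5, so 2 to 12 (section 7.1.4). Share = pre / (pre + post).

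- Nominal: 14 / (14 + 7) = 66.7%
- Lowest, consent at Visit 1: 7 / (7 + 12) = 36.8%
- Highest, consent at Visit 1: 21 / (21 + 2) = 91.3%

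Section 7.1.1 also allows consent up to 3 months before the lumbar puncture. Taking that as 90 days, the share is 90 / 102 = 88.2% with 12 post-dose days and 90 / 97 = 92.8% with 7.

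**2. Plausible number of stray events (assumed rates).** With background AEs at 0.005 to 0.02 per person-day, 12 participants over 14 days give 12 × 14 × 0.005 = 0.84 to 12 × 14 × 0.02 = 3.36 expected pre-dose events. The chance of at least one is 1 − exp(−0.84) = 57% to 1 − exp(−3.36) = 97%.

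**3. Effect on the proportion with any AE.** Let k of the 12 have a pre-dose AE, allocated 6:6 at random and independent of the post-dose risks a (40 IU) and b (80 IU). An arm with risk p then has expected proportion [k/2 + (6 − k/2)p] / 6. The k/2 terms cancel between arms, leaving

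expected difference = (b − a)(1 − k/12).

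The shrinkage is 8.3%, 16.7% and 25% for k = 1, 2, 3. With assumed a = 0.20 and b = 0.50, 30 points become 27.5, 25.0 and 22.5. In participants, the loss is 0.025 × 6 = 0.15 to 0.075 × 6 = 0.45 of one person.

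**4. Effect on the spread.** For post-dose events only, SD = √[(0.2 × 0.8 + 0.5 × 0.5)/6] = 26.1 points. Over the whole window,

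variance = [(2 − a − b)/6]² × k(12 − k)/44 + (6 − k/2)[a(1 − a) + b(1 − b)]/36.

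- k = 1: 0.0469 × 0.250 + 5.5 × 0.41/36 = 0.0744, SD 27.3 points
- k = 2: 0.0469 × 0.455 + 5.0 × 0.41/36 = 0.0783, SD 28.0 points
- k = 3: 0.0469 × 0.614 + 4.5 × 0.41/36 = 0.0801, SD 28.3 points

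Simulation with 400,000 trials per k agreed to within 0.1 point.

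**5. Effect on event counts.** Pre-dose events raise the expected count equally in both arms, so the expected difference stays at 0.50 − 0.20 = 0.30 per participant and gains noise only. The ratio does fall. At an assumed 0.01 background events per person-day it is (0.50 + 0.07)/(0.20 + 0.07) = 2.11 over 7 post-dose days, and (0.50 + 0.21)/(0.20 + 0.21) = 1.73 over all 21 days.

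**The case against.** The strongest reply is that nothing turns on this. The comparison is descriptive and untested, and it is neither the primary nor the secondary endpoint. Even under the assumed inputs the shrinkage is less than half a participant against an SD of about 26 points. That stands, and it is why the point is minor.

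The acute effects of most interest also have their own baselines: nasal irritation is scored before dosing and at 20 and 40 minutes (section 7.3.10), and fingerstick glucose is taken before dosing and at 15 and 45 minutes (section 7.3.6). That stands for those measures, but the irritation scale cannot place a rhinitis that starts on another day.

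The Study Visit Schedule puts randomisation at Visit 2, so an earlier event occurs before the participant has a group and might be left out of a by-group summary. That is a possible reading, but section 12.2 does not say so, and its reference to the whole course of the study points the other way.

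Finally, with 12 participants a line listing with onset dates would settle the matter at reporting. It could, but the plan does not commit to such a split, and one chosen after seeing open-label data is weaker than one written beforehand.

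The dilution formula also has limits. It applies to the proportion with any AE. For one particular AE, k counts only participants who had that same AE before dosing, which will usually be fewer.

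**Conclusion.** The point holds as a minor one. As written, the comparison window takes in time before any insulin, which adds avoidable noise and dilutes proportions and ratios. The window itself follows from the visit schedule; the size of the effect rests on assumed AE rates, because the documents give none. The pharmacokinetic endpoints are unaffected. So is the stopping rule in section 13.2.1, which works from fingerstick glucose and hypoglycaemia symptoms and not from the AE table.

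A reader might infer more than the documents support:

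- **That one dose is favoured.** Section 5 randomises, stratified by gender: "A Block randomization scheme will be employed to ensure that the final group sizes are equivalent". Pre-dose events fall on either arm by chance.
- **That two-thirds of the AEs counted would be pre-dose.** The 67% is calendar time. Events may well cluster around the lumbar puncture and the next-day call, which asks about headache, bleeding and infection (section 7.1.3).
- **That the share is 40% to 50%.** Section 5.2 says "Study participation will last approximately 4-5 weeks", and 14 days over 35 or 28 gives those figures. But they imply 14 to 21 days after dosing, while Visit 3 falls at most about 12 days after.
- **That every measure is diluted.** The expected difference in event counts is not.

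**What to change.** In section 12.2, replace the two AE sentences with wording such as:

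*AEs and SAEs that start or worsen after study drug administration will be categorised and summarised by dose group, and the descriptive comparison of groups will use these events only. Events from consent to dosing will be listed separately with onset date.*

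Leave sections 11.1 and 11.2.2 as they are, so that no safety information is lost. The cost is two sentences and one extra listing, with no new visits, samples or participants. AE onset date is needed throughout, and onset time on the dosing day, because section 7.1.2.1 takes the first CSF sample before the dose and an event from needle placement could therefore come before insulin. The case report forms are not among the documents, so whether they already capture onset time cannot be checked.

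Recording whether the saline dose was taken, and flagging events attributed to the lumbar puncture, are optional extras. Such a flag would rest on investigator judgement, since the trial has no control arm to separate procedure effects from insulin effects.
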